1.4 Rationale/ Novelty

Uproleselan is an E-selectin antagonist. Soluble E-selectin is a significant biomarker for ARDS. Soluble E-selectin also has pro-inflammatory properties further releasing cytokines and promoting its synthesis and the continued influx of neutrophils. Blocking E-selectin with the weak natural carbohydrate ligands containing sialyl Le^x in an animal model of acute lung injury mitigated release of myeloperoxidase, permeability, and hemorrhaging. Small molecule glycomimetic antagonists of E-

selectin (Rivipansel and Uproleselan) are 500- to 1000-fold more potent inhibitors of E-selectin and have shown activity and no measurable toxicity in human clinical trials for other indications. Treatment with these E-selectin inhibitors reduced the levels of soluble E-selectin in the bloodstream which occurs during recovery of ARDS. Thus antagonist of E-selectin Uproleselan (GMI-1271) may be used to treat COVID-19 patients with respiratory symptoms that may lead to ARDS or who have already been diagnosed with ARDS.²² Additionally, endothelial cell infection and endotheliitis have been implicated as a cause of the multiple organ involvement associated with severe COVID-19 and SARS-CoV-2 infection facilitates the induction of endotheliitis in several organs as a direct consequence of viral involvement (as noted with presence of viral bodies) and the host inflammatory response. Therefore, a therapy that targets endothelial cells may play an important protective role in this disease.²¹ This strongly suggests that E-selectin may be an excellent pharmacologic target to reduce progression to ARDS in patients with acute COVID-19 pneumonia.

Endothelial injury is an underlying mechanism that links inflammation and thrombosis in severe COVID-19. The combination of elevated selectin levels, high VWF levels, microvascular thrombosis, and microvascular inflammation all suggest that microvascular injury may be a common trigger for both the inflammatory and thrombotic complications of COVID-19. E-selectin levels were significantly increased in COVID-19 patients requiring hospitalization from ED (pdf attached). Inhibitors of endothelial exocytosis may represent a novel therapeutic approach to the vasculopathy of COVID-19. Inhibition of selectin would block part of the pathway downstream of endothelial injury, including leukocyte rolling and platelet adherence to the vessel wall. We have also measured soluble E-selectin levels in our MM-ICU patients with COVID-19 pneumonia, respiratory failure and ARDS and determined that the levels are significantly increased, and that higher levels and increasing levels over time are associated with death (Figure above).

1.5 Correlative Studies/Special Studies

Biomarkers to evaluate the effects of Uproleselan

The measurement of biomarkers of coagulation, inflammation and angiogenesis in subjects exposed to uproleselan vs. standard of care will enable us to evaluate the effect of Uproleselan on the progression of acute respiratory failure in patients with severe COVID-19 pneumonia. The biomarkers chosen will be indicators of disease severity and progression as well as drug efficacy.

Currently there is no single biomarker that can specifically detect venous thrombosis or its associated inflammatory response in patients. Ramacciotti et al have demonstrated the usefulness of combining circulating biomarkers of coagulation and inflammation to determine a clinical profile that can exclude or confirm if a patient has DVT.³⁰ Therefore in this application we will determine if the previously measured biomarkers which include **D-dimer** as a measure of clot production and breakdown and are significantly elevated in COVID-19 infection and correlate with disease severity,³¹⁻³³ **soluble E-selectin** (E-selectin specifically shown to have highly elevated levels in COVID-19 positive patients transferred into the ICU)²⁶ and **soluble P-selectin**, which are essential glycoproteins expressed during clot formation; **Interleukin-6 (IL-6)** and **interleukin-10 (IL-10)** which are cytokines involved with systemic inflammation that rise with

venous thrombosis and potential players in the cytokine storm phenomenon at play in COVID-19 patients experiencing ARDS. The 4-day change in IL-6:IL-10 ratio, chosen to derive the Dublin-Boston score, was associated with more severe outcomes with COVID-19;³⁴ **Angiopoietin-2**, an angiogenic growth factor affecting cardiovascular remodeling and indicator of endothelial cell activation shown to be predictive of severe COVID-19 infection,^{26, 35} and **TNF-alpha** an acute phase proinflammatory cytokine which may be another indicator of disease severity during COVID-19 infection.³⁶

2. STUDY OBJECTIVES

2.1 Primary Objective

To determine the safety of uproleselan in patients with severe COVID-19 pneumonia.

2.2 Secondary Objectives

To evaluate if treatment with uproleselan administered intravenously in addition to the best available therapy according to institutional guidelines is able to reduce the progression of acute respiratory failure, in patients with severe COVID-19 pneumonia.

- To evaluate overall survival and all-cause mortality at day 15 and 28.
- To evaluate changes in the COVID ordinal outcomes scale.
- To assess adverse events to evaluate the safety of uproleselan.
- To assess ventilator-free days, ICU-free days, oxygen, vasopressor free days.
- To evaluate changes in D-dimer.

Exploratory Objectives:

- To examine the correlation of plasma soluble E-selectin concentrations with clinical outcomes.
- To examine the correlations of other biomarkers of interest with clinical outcome.

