Phase	Phase I (proof of concept, prospective, interventional, open label single group assignment)
Methodology	Open label with matched de-identified retrospective control cohort
Study Duration	Approximately 24 months
Study Center(s)	Single Center in the United States – University of Michigan, Ann Arbor
Objectives	
Primary Objective:
 
Safety of uproleselan in patients with severe COVID-19 pneumonia.
 
Secondary Objectives:
 
To evaluate if treatment with uproleselan administered intravenously in addition to the best available therapy according to institutional guidelines is able to reduce the progression of acute respiratory failure, in patients with severe COVID-19 pneumonia.
 
 ● To evaluate overall survival and all-cause mortality at day 15 and 28. ● To evaluate changes in the COVID ordinal outcomes scale. ● To assess adverse events to evaluate the safety of uproleselan. ● To assess ventilator-free days, ICU-free days, oxygen, vasopressor free days. ● To evaluate changes in D-dimer. 
Exploratory Objectives:
 
 ● To examine the correlation of plasma soluble E-selectin concentrations with clinical outcomes. ● To examine the correlations of other biomarkers of interest with clinical outcome.
Number of Subjects	15 subjects will be enrolled in the experimental cohort to receive uproleselan. with 1:1 matched de-identified retrospective control cohort. (n=15)
Inclusion Criteria	
 1. Adults, ages 18 – 85 years. 2. Willing and able to provide informed consent prior to performing study procedures unless they have a legally authorized representative (LAR). 3. Documented COVID-19 pneumonia: defined as upper respiratory tract specimen (nasopharyngeal swab (NPS) or viral throat swab) positive for COVID-19 and imaging (CXR/CT scan) suggestive of COVID-19 pneumonia. 4. Confirmed coronavirus (SARS-CoV-2) infection, enrolled ≤ 48 hours of beginning oxygen need for COVID-19+ confirmed hospital admission.

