
Exclusion Criteria
	
 1. In the opinion of at least one investigator, unlikely to survive for >48 hours from screening. 2. Severe chronic respiratory disease (e.g. COPD or other) requiring supplemental oxygen and/or having required mechanical ventilation pre-COVID-19 infection. 3. Concurrent enrollment in a COVID-related interventional drug trial. Use of remdesivir, steroids, and convalescent plasma are permitted along with other standard of care therapies for COVID. 4. Currently on invasive mechanical ventilation. 5. Hypotension defined as systolic blood pressure < 90 mmHg on two sequential readings at least 4 hours apart. 6. Total Bilirubin ≥ 3 x upper limit of normal (ULN), Creatinine Clearance ≤ 30 mL/min/1.73m². 7. Pregnant or breastfeeding. 8. Known diagnosis of an acute thrombosis on admission. 9. Concurrent dual antithrombotic therapy (aspirin or P2Y12 inhibitor plus anticoagulation to treat deep venous thrombosis or pulmonary embolism (single antiplatelet or anticoagulant agent at prophylactic dose is permitted). 10. Concomitant use of thrombolytic therapy. 11. Concomitant therapeutic systemic anticoagulant therapy (e.g. heparin, warfarin, direct thrombin inhibitors and direct factor Xa inhibitors). 12. History of recent major bleeding, defined in accordance with the criteria of the International Society on Thrombosis and Hemostasis (ISTH). 13. History of bleeding disorder thought to impose excessive bleeding risk, as per investigator discretion. 14. Hemodynamic instability, defined as inability to maintain mean arterial pressure. 15. Hypersensitivity to the active substance or to any of the excipients of uproleselan.

	16. Any physical examination findings and/or history of any illness that, in the opinion of the investigator, might confound the results of the study or pose an additional risk to the patient by their participation in the study.
Study Product(s), Dose, Route	Uproleselan 20mg/kg BID, up to a maximum dose of 2500mg, IV infused over 20 minutes on days 1-7.
Duration of Administration	Uproleselan: 20-minute IV infusion BID on days 1-7.
Control	1:1 matched de-identified retrospective control cohort (patients enrolled during the same period with similar severity, not enrolled in another interventional trial, receiving best available therapy according to institutional guidelines).

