3.2 Secondary Endpoints

- Reduction in the progression to acute respiratory failure [Time Frame: 15 days for primary endpoint].
- Patients with a baseline PaO₂/FiO₂ ≥ 200: progression of respiratory failure is defined by:
 - a. severe gas transfer deficit (PaO₂/FiO₂ < 200);
 - b. persistent respiratory distress while receiving oxygen (persistent marked dyspnea, use of accessory respiratory muscles, paradoxical respiratory movements);
- The rate will be calculated as the proportion of patients who experienced at least one of the events above by day+15 from treatment start.

- Reduction in the progression to acute respiratory failure [Time Frame: 28 days].
- Overall survival and all-cause mortality (day 15, day 28).
- Time to improvement in oxygenation for at least 48 hours. Improvement in oxygenation is defined as an increase in PaO₂/FiO₂ of 50 (or greater) compared to the nadir of PaO₂/FiO₂.
- Number of patients requiring mechanical ventilation, if not on mechanical ventilation at study entry.
- Change in the WHO COVID-19, “8-point ordinal scale” from study entry to day 28 (Table 1). To be assessed on day 3, day 8, day 15, day 28.
- Duration of hospitalization and duration of ICU care.
- Toxicity assessment (including incidence of grade 3-5 hemorrhagic events).
- Change in D-dimer [Time Frame: baseline, study day 3, day 8, day 15, and day 28]. Changes in plasma D-dimer level compared with baseline at enrollment.
- Decrease or Change in IL-6:IL-10 ratios.
- Free-Days- at day 28
 - Oxygen
 - Ventilator
 - Vasopressor
 - ICU
 - Hospitalization

Table 1: WHO Ordinal Scale Ordinal Score

Patient State	Descriptor	Score
Ambulatory	No limitation of activities	1
	Limitations of activities	2
Hospitalized (mild disease)	No oxygen therapy	3
	Oxygen by mask or nasal prongs	4
Hospitalized (severe disease)	Non-invasive ventilation or high-flow oxygen	5
	Intubation and mechanical ventilation	6
	Mechanical ventilation + additional organ support – pressors, RRT, ECMO	7
Dead	Death	8

Exploratory Endpoints

- Soluble E-selectin and P-selectin levels compared with baseline at enrollment.
- Thrombosis free days (clinically defined) at day 28.
- Change in other cytokine levels, endothelial or leukocyte activation (day 1, 15, 28) in IL-6, IL-10, Angiopoietin-2, and TNF-alpha

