12 STATISTICAL CONSIDERATIONS

12.1 Study Design/Study Endpoints

This is a prospective, interventional, single-arm, open label trial, with 1:1 matched de-identified retrospective control cohort. Study subjects will receive uproleselan IV BID x 7 days. 15 patients who consent to drug administration will be enrolled in the treatment arm.

Primary Endpoints: Safety

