12.3 Data Analyses Plans

Descriptive statistics will be calculated for quantitative safety data, as well as change from baseline. Frequency counts will be compiled for classification of qualitative safety data.

Secondary endpoints include reduction in the progression to acute respiratory failure. For patients with a baseline PaO₂/FiO₂ \geq 200: progression of respiratory failure is defined by:

- severe gas transfer deficit (PaO₂/FiO₂ < 200);
- persistent respiratory distress while receiving oxygen (persistent marked dyspnea, use of accessory respiratory muscles, paradoxical respiratory movements);

The rate will be calculated as the proportion of patients who experienced at least one of the events above by day+15 from treatment start.

There are many other secondary endpoints, but two of the most important are: (i) Day 28 overall survival and (ii) Day 28 ventilator free survival, both of which are binary endpoints. Day 28 overall survival will be summarized by the proportion of the twelve patients who are alive at Day 28 after starting treatment, and Day 28 ventilator-free survival will be summarized by the proportion of the twelve patients who are both alive and not using a ventilator at Day 28 after starting treatment. Both proportions will be

accompanied by an exact 95% confidence interval. All other secondary endpoints will be collected and assessed.

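### The lead secondary objective and endpoint are worded as a reduction in progression to respiratory failure, but the only stated analysis is a treated-arm proportion with no interval, benchmark or contrast with the matched controls

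*Combined protocol and SAP*

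**What the plan says.** - **Objective (synopsis; Section 2.2).** The first secondary objective is to evaluate whether uproleselan, given on top of background care, "is able to reduce the progression of acute respiratory failure".
- **Endpoint (Section 3.2).** It is listed as "Reduction in the progression to acute respiratory failure [Time Frame: 15 days for primary endpoint". The events are introduced by "Patients with a baseline PaO₂/FiO₂ ≥ 200: progression of respiratory failure is defined by"; no event is defined for patients who start below 200. The same naming recurs in Sections 5.2.1, 7.2, 12.1.3 and 12.3.
- **Analysis (Section 12.3).** "The rate will be calculated as the proportion of patients who experienced at least one of the events above by day+15 from treatment start". The synopsis and Sections 3.2, 5.2.1, 7.2 and 12.1.3 say the same and add nothing.
- **Design (Section 12.1).** "This is a prospective, interventional, single-arm, open label trial, with 1:1 matched de-identified retrospective control cohort". The synopsis gives the size: "15 subjects will be enrolled in the experimental cohort to receive uproleselan. with 1:1 matched de-identified retrospective control cohort. (n=15". It describes the controls as "patients enrolled during the same period with similar severity, not enrolled in another interventional trial", on best available therapy. It lists no matching variables.
- **Use of the controls.** The statistical paragraph of the synopsis contrasts biomarker levels with the control cohort, graphically and with simple statistics. Section 1.5 also speaks of biomarkers against standard of care. Section 12.3 does not mention the controls.
- **Intervals.** Section 12.3 attaches an exact 95% confidence interval to Day 28 overall survival and Day 28 ventilator-free survival only.

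**The concern.** A reduction is a statement about two quantities, and the planned analysis produces one. The design includes a cohort that could supply the second, yet the plan never connects it to progression. If nothing changes, the trial's lead efficacy question ends with a rate and no effect estimate. Any later comparison with the controls would have to be devised without a prespecified method, in an open-label study whose control outcomes lie in existing records. With 15 per cohort, the choice of interval method alone can decide whether zero is excluded, as the working shows, so the method should be fixed in advance.

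**Working it through.** **1. Question against analysis.** The plan states no progression rate, effect size, alpha or power, so there is no figure to reproduce.

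| Element | What the plan gives for progression |
|---|---|
| Question | Does treatment reduce it? (Section 2.2) |
| Reference group | Matched controls exist (synopsis; Section 12.1), not named in the analysis |
| Historical benchmark | None; the 70% in Section 13 is a mortality rate for a stopping rule |
| Estimator | Treated-arm proportion by Day 15 (Section 12.3) |
| Interval | None |

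No row supplies a difference or ratio.

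**2. Precision of the stated estimator.** Event counts are assumed. Exact limits for x of n: lower = Beta quantile 0.025 with parameters (x, n−x+1); upper = Beta quantile 0.975 with parameters (x+1, n−x).

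| x/n | Exact 95% CI |
|---|---|
| 3/15 | 4.3% to 48.1% |
| 4/15 | 7.8% to 55.1% |
| 5/15 | 11.8% to 61.6% |
| 8/15 | 26.6% to 78.7% |
| 3/10 (if only 10 start at PaO2/FiO2 of 200 or more) | 6.7% to 65.2% |

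**3. What a paired contrast would look like.** All pair tables are assumed; the documents give none. Cells are a (both progress), b (treated only), c (control only), d (neither), with n = 15. The difference is D = p1 − p2 = (b − c)/n. With Wilson limits (l1, u1) for treated and (l2, u2) for control, the paired Newcombe limits are:

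- lower = D − √[(p1−l1)² − 2φ(p1−l1)(u2−p2) + (u2−p2)²]
- upper = D + √[(u1−p1)² − 2φ(u1−p1)(p2−l2) + (p2−l2)²]

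Here φ = (ad − bc)/√(product of the four margins). With the continuity correction, a positive numerator is reduced by n/2 = 7.5 and set to zero if that makes it negative.

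Worked case (2,1,6,6): 3/15 against 8/15, D = (1 − 6)/15 = −0.333. Wilson limits are 0.070 to 0.452 and 0.301 to 0.752. ad − bc = 12 − 6 = 6, below 7.5, so the corrected φ = 0. Lower = −0.333 − √(0.130² + 0.219²) = −0.587. Upper = −0.333 + √(0.252² + 0.232²) = +0.009.

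| Assumed table | Margins | Correction | D | 95% CI (points) |
|---|---|---|---|---|
| (2,2,4,7) | 4/15 vs 6/15 | yes | −13 | −42 to +19 |
| (2,1,6,6) | 3/15 vs 8/15 | yes | −33 | −59 to +1 |
| (2,1,6,6) | 3/15 vs 8/15 | no | −33 | −57 to −1 |
| (3,0,5,7) | 3/15 vs 8/15 | yes (φ = 13.5/√2016 = 0.30) | −33 | −55 to −5 |

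The last three rows share the same two rates. Whether zero is excluded depends on the pairing and on the correction.

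**4. Estimation, not testing.** Assume a control progression rate of 30% to 70%, halved by treatment, with independent groups because no within-pair correlation is given. Two-sided Fisher power at 0.05 with 15 per group, summed over the binomial outcomes, is 8% to 32%.

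**5. Can the contrast be run on the text as it stands?** Not yet. The clock runs from treatment start, which controls do not have. Entry criterion 6 admits PaO2/FiO2 of 300 or less, or other signs, so some patients may start below 200 with no defined event. Section 6.1.1 obtains blood gases only as clinically indicated, even in treated patients. Nothing shows that the control records hold serial PaO2/FiO2 or bedside signs of distress.

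**The case against.** The strongest reply is that this is a pilot. Safety is the only primary endpoint (Sections 3.1 and 12.1), Section 12.2 says the sample size has no power basis, and no decision rests on progression. On that view the objective is loosely worded and rewording it would suffice. Much of this stands. Pilot status excuses low power, and rewording alone would remove the mismatch. It does not make a treated-arm rate answer a question about reduction. Nor can the comparison be taken as implied: the synopsis spells out a control contrast for biomarkers and, in the same paragraph, gives only a proportion for progression.

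A second reply is that a matched contrast could mislead, since it stays confounded and may rest on differently ascertained outcomes. That also stands, and it governs how the contrast is set up and labelled.

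A reader might infer three stronger things that the documents do not support:

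- **That the objective has no estimate at all.** It has a treated-arm rate; what it lacks is an effect estimate.
- **That survival and ventilation share the fault.** They are worded without a comparison (Sections 2.2 and 3.2), and Day 28 survival and ventilator-free survival already carry exact intervals.
- **That 3/15 against 8/15 must leave an interval covering zero.** The working shows it need not.

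**Conclusion.** The point holds for progression to acute respiratory failure and is limited to it. The objective and endpoint ask about a reduction, the plan calculates one proportion, and the matched cohort is contrasted only for biomarkers. This conclusion comes from the text and needs no numerical assumption. The figures show scale only: a treated-arm rate of 4/15 would carry an interval about 47 points wide (55.1 − 7.8 = 47.3), and every paired example depends on an assumed pair table. The change is worth making, because this is the lead efficacy question and the comparator is already planned. It does not touch the primary safety analysis. The phrase in Section 3.2 tying the 15-day window to a primary endpoint might suggest that progression is primary; Sections 3.1 and 12.1 name safety alone.

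**What to change.** **If the control records can support the endpoint**, revise Section 12.3 to:

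- report the treated-minus-matched-control difference in Day 15 progression with a paired 95% CI whose method, including any continuity correction, is named in advance;
- label it descriptive and hypothesis-generating;
- apply the same event definition and the same baseline PaO2/FiO2 ≥ 200 denominator to both cohorts, and state how many pairs are evaluable;
- list the matching variables and give controls an index date equivalent to treatment start, for example the matched time since supplemental oxygen began.

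Restate the objective as estimating the difference in progression.

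**If the records cannot support it**, reword the objective and endpoint as estimating the progression rate in treated patients, with an exact 95% CI, and make no claim of reduction.

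Paired contrasts for survival and ventilation are optional.

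**Cost.** No new treated patients. The second route is wording plus one interval. The first also needs a check of what the control records contain, a matching specification and abstraction of control outcomes. The interval will be wide, fewer than 15 pairs may be evaluable, and the contrast stays confounded.

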3. ENDPOINTS

3.1 Primary Endpoints: Safety of uproleselan in patients with severe COVID-19 pneumonia.

3.2 Secondary Endpoints

- Reduction in the progression to acute respiratory failure [Time Frame: 15 days for primary endpoint].
- Patients with a baseline PaO₂/FiO₂ ≥ 200: progression of respiratory failure is defined by:
 - a. severe gas transfer deficit (PaO₂/FiO₂ < 200);
 - b. persistent respiratory distress while receiving oxygen (persistent marked dyspnea, use of accessory respiratory muscles, paradoxical respiratory movements);
- The rate will be calculated as the proportion of patients who experienced at least one of the events above by day+15 from treatment start.

- Reduction in the progression to acute respiratory failure [Time Frame: 28 days].
- Overall survival and all-cause mortality (day 15, day 28).
- Time to improvement in oxygenation for at least 48 hours. Improvement in oxygenation is defined as an increase in PaO₂/FiO₂ of 50 (or greater) compared to the nadir of PaO₂/FiO₂.
- Number of patients requiring mechanical ventilation, if not on mechanical ventilation at study entry.
- Change in the WHO COVID-19, “8-point ordinal scale” from study entry to day 28 (Table 1). To be assessed on day 3, day 8, day 15, day 28.
- Duration of hospitalization and duration of ICU care.
- Toxicity assessment (including incidence of grade 3-5 hemorrhagic events).
- Change in D-dimer [Time Frame: baseline, study day 3, day 8, day 15, and day 28]. Changes in plasma D-dimer level compared with baseline at enrollment.
- Decrease or Change in IL-6:IL-10 ratios.
- Free-Days- at day 28
 - Oxygen
 - Ventilator
 - Vasopressor
 - ICU
 - Hospitalization

Table 1: WHO Ordinal Scale Ordinal Score

Patient State	Descriptor	Score
Ambulatory	No limitation of activities	1
	Limitations of activities	2
Hospitalized (mild disease)	No oxygen therapy	3
	Oxygen by mask or nasal prongs	4
Hospitalized (severe disease)	Non-invasive ventilation or high-flow oxygen	5
	Intubation and mechanical ventilation	6
	Mechanical ventilation + additional organ support – pressors, RRT, ECMO	7
Dead	Death	8

Exploratory Endpoints

- Soluble E-selectin and P-selectin levels compared with baseline at enrollment.
- Thrombosis free days (clinically defined) at day 28.
- Change in other cytokine levels, endothelial or leukocyte activation (day 1, 15, 28) in IL-6, IL-10, Angiopoietin-2, and TNF-alpha

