Statistical Methodology	
This is a pilot proof of concept feasibility study. 15 patients who consent to drug administration will be enrolled in the treatment arm. The sample size determination was not based on statistical power analysis but is large enough to provide adequate information regarding safety, and will contribute to the design of subsequent studies, and is the number of patients that we can expect to accrue in the current setting of the SARS-CoV2 pandemic.
 
Descriptive statistics will be calculated for quantitative safety data, as well as change from baseline. Frequency counts will be compiled for classification of qualitative safety data.
 
Regarding secondary endpoints, the efficacy of uproleselan in prevention of acute respiratory failure, the rate will be calculated as the proportion of patients who experienced at least one of the events above by day+15 from treatment start. The biomarkers will be evaluated for trends at the sample collection time points and contrasted graphically and with simple statistics to the levels observed for control cohort subjects, as the study is not powered for this endpoint.

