4.1 Inclusion Criteria

1. Adults, ages 18-85 years.
2. Willing and able to provide informed consent prior to performing study procedures unless they have a legally authorized representative (LAR).
3. Documented COVID-19 pneumonia: defined as upper respiratory tract specimen (nasopharyngeal swab (NPS) or viral throat swab) positive for COVID-19 and/or imaging at computed tomography scan suggestive of COVID-19 pneumonia.
4. Confirmed coronavirus (SARS-CoV-2) infection admitted to the hospital, enrolled ≤ 48 hours of need for supplemental oxygen.
5. Currently hospitalized requiring supplemental oxygen.
6. Have severe COVID-19 according to the WHO Interim Guidance with confirmation by real-time RT-PCR assay. The enrollment criteria with one of the following: respiratory distress, RR ≥ 30 beats/min; oxygen saturation level less than 93% in resting state; or partial pressure of oxygen (PaO₂)/oxygen concentration (FiO₂) ≤ 300 mmHg.
WHO, Clinical management of severe acute respiratory infection when Novel coronavirus (nCoV) infection is suspected: Interim guidance. [https://www.who.int/publications-detail/clinical-management-of-severe-acute-respiratory-infectionwhen-novel-coronavirus-\(ncov\)-infection-is-suspected](https://www.who.int/publications-detail/clinical-management-of-severe-acute-respiratory-infectionwhen-novel-coronavirus-(ncov)-infection-is-suspected).
7. Willing and able to participate in all required evaluations and procedures.

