6.1.1 Procedures during Study Drug Treatment Visits

If a laboratory parameter has been obtained within 48 hours prior to study enrollment, it does not need to be repeated for study purposes and will be considered the *baseline* value. Following the last day of study, no further “study related” blood tests will be obtained.

Guidelines for monitoring hematologic and coagulation parameters were derived from Thachil, J., et al., *ISTH interim guidance on recognition and management of coagulopathy in COVID-19*. *J Thromb Haemost*, 2020. **18**(5): p. 1023-1026.⁴²

- **Pulmonary Indices:** Pulmonary parameters will be recorded daily for subjects from the time of study entry to cessation of study drug therapy. Pulmonary assessment will include a subject’s current level of supplemental oxygen support (%FiO₂), current modality of support (mechanical ventilation, BiPaP, CPAP, nasal cannula, or none), and the results of any chest radiographs (if performed) that day. For patients that remain hospitalized on day 15 or 28 of study, pulmonary indices will also be made at that time point. Blood gas values will be obtained as clinically indicated. Scoring from the WHO COVID Ordinal Scale (Table 1) will be determined as indicated by study investigators or study coordinators.
- **Hematologic parameters:**
A complete blood count including platelets (CBCP) should be obtained at baseline (study entry), and daily until cessation of study therapy. Additional blood counts may be obtained as clinically indicated.
- **Chemistries:**
Serum chemistries (Electrolytes, BUN, creatinine, liver panel) should be obtained at baseline (study entry), and daily until cessation of study therapy. Additional chemistries should be obtained as clinically indicated.
- **Coagulation Labs:**
D-dimer, Prothrombin time (PT), activated partial thromboplastin time (aPTT), and serum fibrinogen should be obtained at baseline (study entry). Additional D-dimer, PT, and serum fibrinogen testing may be obtained as clinically indicated.
- **Serologic Cytokine Profiles:** Biomarkers will be drawn on day 0-1 pre-study drug administration, days 1-7, day 15, and day 28. These will be used to measure e-selectin levels and are not for safety labs. Due to current hospital understaffing, blood draws will occur as staffing permits. Missed blood draws will not be counted as protocol deviations.

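### The Day 15 progression rate is defined only for patients entering at PaO2/FiO2 of 200 or more, names no denominator, and counts a death or intubation as no progression unless criterion (a) or (b) was recorded

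*Combined protocol and SAP*

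**What the plan says.** Section 3.2 opens the definition with "Patients with a baseline PaO₂/FiO₂ ≥ 200: progression of respiratory failure is defined by" and then lists (a) a fall in the ratio below 200 and (b) persistent respiratory distress while on oxygen. Sections 5.2.1, 7.2, 12.1.3 and 12.3 repeat this. No section gives a definition for a baseline below 200, and none excludes such patients from the analysis.

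The summary measure in section 12.3 is: "The rate will be calculated as the proportion of patients who experienced at least one of the events above by day+15 from treatment start". The synopsis (Statistical Methodology) refers to "the efficacy of uproleselan in prevention of acute respiratory failure, the rate will be calculated as the proportion of patients" with at least one of the events above, but it lists no events and does not mention the limit of 200.

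Four other parts of the plan bear on this:

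- **Eligibility (4.1, item 6).** One of several alternative ways in is "partial pressure of oxygen (PaO₂)/oxygen concentration (FiO₂) ≤ 300 mmHg". There is no lower limit. Respiratory distress or rate, or low saturation, is enough alone. Section 4.2 excludes invasive ventilation only.
- **Objective (2.2).** The question is whether treatment "is able to reduce the progression of acute respiratory failure, in patients with severe COVID-19 pneumonia".
- **Measurement (6.1.1 and Table 4).** "Blood gas values will be obtained as clinically indicated". Table 4 marks a baseline arterial gas, but note a leaves arterial gases to routine care and allows a venous gas instead. Under note d, pulmonary indices stop at discharge.
- **Neighbouring endpoints.** Mortality is a separate item in section 3.2, as is "Number of patients requiring mechanical ventilation, if not on mechanical ventilation at study entry". Section 12.3 summarises Day 28 ventilator-free survival as the proportion "both alive and not using a ventilator at Day 28 after starting treatment".

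**The concern.** The endpoint does not fit the population enrolled. A patient admitted with a ratio below 200, or with no arterial baseline, is eligible and treated and falls under the objective, yet has no event that could count as progression.

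The rate sentence names no analysis set. Two analysts could follow the text and report different percentages from the same patients.

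The event list contains neither death nor intubation. Many patients who die or are intubated will first meet (a) or (b), but the schedule does not ensure that this is recorded. Applied literally, the rule then places the worst outcomes with the non-progressors.

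Component (b) has no new-onset requirement, although respiratory distress is an entry criterion, so a patient can meet it from the start. No rule covers patients discharged before Day 15 or subjects removed and replaced under section 5.7.

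This rate is the direct measure of the opening secondary objective and the only item under 7.2 Efficacy. The trial is open label and is meant to inform later studies. The scoring should not be left to the analyst, and a matched control cohort could be scored differently.

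**Working it through.** The plan gives no assumed rate, target or interval for this endpoint, so there is no figure to reproduce. The only input from the documents is N = 15 treated (section 12.2). The number entering below 200 and all event counts are assumptions, shown over a range. Intervals are exact (Clopper-Pearson) 95%.

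**Step 1: denominator.** Let k patients enter below 200 and let x of the other 15 − k have a recorded (a) or (b). The subgroup reading gives x/(15 − k). The all-patients reading gives x/15.

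| k | x | Subgroup reading | All-patients reading |
|---|---|---|---|
| 2 | 4 | 4/13 = 30.8% (9.1 to 61.4) | 4/15 = 26.7% (7.8 to 55.1) |
| 5 | 3 | 3/10 = 30.0% (6.7 to 65.2) | 3/15 = 20.0% (4.3 to 48.1) |
| 8 | 2 | 2/7 = 28.6% (3.7 to 71.0) | 2/15 = 13.3% (1.7 to 40.5) |

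The readings differ by 30.8 − 26.7 = 4.1, 30.0 − 20.0 = 10.0 and 28.6 − 13.3 = 15.3 percentage points. The gap comes only from the unstated denominator.

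**Step 2: can a death or intubation escape (a) and (b)?** Component (a) needs a PaO2. Gases after baseline are unscheduled, and the pulmonary indices in section 6.1.1 are inspired oxygen, support modality and any radiograph, not PaO2. Component (b) is clinical, but physical examinations are scheduled daily on Days 1 to 7 only. Pulmonary indices are taken on those days and again on Days 8, 15 and 28 in patients still in hospital. Nothing that would capture (a) or (b) is scheduled on Days 9 to 14. Death is not a remote case in this plan: section 13 takes 70% as the historical Day 14 mortality and 50% as the contrasting scenario.

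**Step 3: size per missed patient.** Each such death or intubation, if counted, would move the rate by 1/15 = 6.7 points over all treated, or 1/10 = 10 points in a subgroup of ten. If the patient entered below 200, the subgroup reading would not move at all.

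**Step 4: worked example.** Take k = 5 and x = 3. Add three deaths or intubations by Day 15 without a recorded (a) or (b): two among the five below 200 and one among the other ten.

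- Plan as written: still 3/10 = 30.0% or 3/15 = 20.0%.
- Counting the one case within the subgroup only: 4/10 = 40.0% (12.2 to 73.8).
- Proposed rule over all treated: (3 + 1 + 2)/15 = 6/15 = 40.0% (16.3 to 67.7). This assumes the three recorded events also qualify under the new rule.

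**The case against.** The strongest reply has five parts.

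- **The subgroup reading is the natural one.** In sections 7.2, 12.1.3 and 12.3 the rate sentence follows directly on the restricted definition, and the synopsis can be applied only by importing that definition. This stands as a preference between readings. It does not supply a stated analysis set, and the subgroup reading leaves the objective wider than its endpoint.
- **The limit of 200 has a logic.** A fall below 200 cannot be a new event for someone already below it. That is true of (a). It does not explain why (b), death or intubation should not count for those patients.
- **No sentence says a death is a non-event.** Correct: this follows from a rule that counts only listed events. Some such patients will have (a) or (b) recorded first, so the gap concerns the remainder.
- **The outcomes said to be missed are reported elsewhere.** Mortality and ventilation are separate endpoints for all patients, section 12.3 singles out Day 28 survival and ventilator-free survival, and note f provides contact on Days 15 and 28. This stands, and it limits the harm to this one rate.
- **The 40% example changes population, definition and denominator together, and the intervals overlap heavily.** Also fair. With 15 patients no version is precise. The issue is what the reported percentage means.

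**Conclusion.** The concern holds. The limit of 200 without an eligibility floor and the missing analysis set are explicit in the text. The scoring of deaths and intubations follows from applying the stated event list literally.

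Under the assumed counts, the denominator alone moves the rate by about 4 to 15 points. Each uncounted death or intubation is worth 6.7 points over 15 patients or 10 points over 10. These sizes rest on the assumed numbers entering below 200 and the assumed event counts, which the documents do not give.

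The rate is secondary and descriptive, no stopping rule uses it, and death and ventilation are reported separately. It should be fixed, but it does not threaten the primary safety objective.

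**What to change.** Define progression by Day 15, and likewise by Day 28, for all treated patients, with all treated as denominator. Count any of:

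1. death;
2. invasive ventilation;
3. persistent respiratory distress that is new or worse than at baseline;
4. an arterial PaO2/FiO2 below 200, only where the arterial baseline was 200 or more.

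Handling rules:

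- A missing baseline ratio drops item 4 only.
- Patients discharged alive are non-progressors unless the chart or the Day 15 or Day 28 contact shows an event.
- Treated subjects who are removed and replaced stay in the denominator. If their status is unknown, list them and give the rate with them as events and as non-events.
- Report the present definition in the subgroup at 200 or above, with its n, as supportive.
- Apply the same rule to the control cohort if the rate is compared.

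**Cost.** The wording changes in sections 3.2, 5.2.1, 7.2, 12.1.3 and 12.3 and in the synopsis. Death and ventilation are already collected. New or worse distress needs chart review against baseline, in the controls too if they are compared. No new test or visit is needed. The rate becomes less specific to gas exchange and probably higher, items 1 and 2 overlap endpoints already reported, and patients below 200 have three routes to an event instead of four.
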